18.8.3 Linear Multilevel Models

Analyses will focus on longitudinal trajectories of change for outcomes specified in objectives 1-3. Generalized linear multilevel models will evaluate change as a function of time, treatment, and the interaction of treatment and time after controlling for stratification variables (i.e. site and baseline severity as measured by the MSOFA < 4 or \geq 4). Analyses will utilize Bayesian inference. Prior distributions will be neutral (centered on the null hypothesis) and weakly informative as described by Gabry and Goodrich (2020). This will have the benefit of regularizing any parameter estimates and render more conservative estimates of effect size. Regarding priors essentially as a set of assumptions, we will evaluate the robustness of our analytic conclusions to alternative prior specifications with varying degrees of regularization/skepticism (Gelman, 2007; Spielgelhalter, 2004).

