5.2. Assessment of Safety

- Incidence of adverse events (AEs)
- Incidence of serious AEs (SAEs)
- Incidence of thromboembolic events
- Creatinine, bilirubin, AST and ALT, hemoglobin

In addition to the ongoing and final safety assessments through the course of the trial, a detailed review of safety by the DSMB will follow the ascertainment of the 14-day outcomes on the first 30 and 120 patients. After 30 and 120 patients have received treatment and have completed their day 14 event, enrollment will be suspended (suspension of enrollment will occur at n = 30, based on DSMB recommendation, enrollment will continue during the safety analysis at n = 120). An interim blinded safety report will be sent to the DSMB. Enrollment will continue according to DSMB recommendations. The DSMB will provide a report to the UTHealth COVID-19 Research Workgroup and UTHealth IRB to consider further patient screening and enrollment.

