8.4. Data Collection

Refer to *Appendix 1 (Schedule of Activities)* for detailed timing and frequency of the below activities:

- Informed consent
- Demographic and contact information
- Oxygen saturation by pulse oximetry
- Pregnancy test (collected only at baseline)

٠

- Hemoglobin, creatinine, liver function test (AST, ALT, Bilirubin) at baseline, day 7, day 14 and during long term follow up visits at 6mo, 12mo and 24mo (If the patient remains hospitalized after 14 days, or the drug is discontinued for any reason, creatinine and hemoglobin lab values will be collected for up to 2 days following the last dose, again ceasing upon discharge.)
- Height, weight, BMI
- Eligibility, at baseline
- Randomization
- Blood biomarkers (during hospitalization only) \circ Baseline, Day 7 and Day 14 (10 cc each collection)
- Urine biomarkers (during hospitalization only)
 o Baseline, Day 7 and Day 14 (5 cc each collection)
- Medical/Medication history
- Study medication dosing
- AE and SAEs
- Concomitant medications and COVID-19 specific treatment other than vitamins and minerals
- Modified SOFA, daily until discharge, & at Day 7, 14, and 28, with discharged patients receiving a score of 0 and deceased patients receiving a score of 20.
- NIAID-OS, daily and until discharge and at Day 7, 14, and 28
- For patients who are discharged, before or after completing 14 days of in-hospital treatment, a phone visit at day 7, 14, and 28 after randomization will be conducted to collect serious adverse events and NIAID-OS score.

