18.1 Long-Term Follow-up

[figure not shown]
The purpose of this amendment is to characterize the long-term effects on COVID-19 survivors who were hospitalized with SARS-CoV-2 and treated with either a HIF activator vadadustat or placebo. Specifically, we will 1) characterize the occurrence of long-term COVID-19 sequelae in a well-described patient cohort and 2) address the hypothesis that vadadustat would attenuate or prevent the long-term disease sequelae of SARS-CoV-2.

18.2 Study Objectives.

Primary: Evaluation of pulmonary capacity as a function of treatment, time and the interaction of treatment and time.

Secondary: Evaluate cardiac, hepatic and renal outcomes, quality of life, and long-term neurocognitive impairment of COVID-19 patients treated with either vadadustat or placebo

18.3 **Study Diagram.**

18.4 **Study Population.**

Eligibility Criteria

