18.4.2 Exclusion Criteria

- Patients who were enrolled in the vadadustat study but withdrew before taking the 1st dose of the study drug.
- Patients who were enrolled in the vadadustat study but did not consent for an extended follow-up.
- Patients who do not speak English or Spanish. •

18.5 **Data Collection.**

The following will be collected on the 6th, 12th and 24th month follow-up.

Informed consent for the extended follow-up shall be referenced to the IRB approved ICF of vadadustat study starting February 5, 2021 wherein patients have agreed to participate in this long-term study.

For those patients consented prior to February 5, 2021, please refer to Section 18.9 of the study protocol for the reconsenting process.

- Body Mass Index, height, weight •
- Medication History
- Tobacco use •
- Past Medical History
- Laboratory Tests: ALT, AST, Total Bilirubin, Creatinine, and Hemoglobin. •
- Cardiac, Renal and Lung Biomarkers (Blood and urine) •

Pulmonary Function test

- Transthoracic echocardiography (TTE)
- Lung ultrasound
- PROMIS Scale v1.2 Global Health Survey
- MoCA Test (Montreal Cognitive Assessment)

18.6 Study Procedures.

Each study participant will undergo the following procedures on 6th, 12 and 24th month follow- up. There is a one (1) month window to complete each follow up appointment once a patient reaches their long term follow up due date. This one-month window provides flexibility to schedule and accommodate both the patient and the clinical teams' availability. If a patient cannot be scheduled within one month of their follow up date, this will be deemed a loss to follow up and documented in RedCAP accordingly.

18.6. 1 Sample collection processing

Blood and urine samples will be collected at our Clinical Research Unit (CRU) and processed using standard protocols. Blood specimens will be collected from the patient (biomarkers and laboratory specific tests) and urine over the course of the visit. Universal precautions and institutional biosafety procedures will be followed.

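### Section 18.8.3 gives pre-treatment laboratory values no stated role in the long-term models, although the same tests are taken at baseline and at 6, 12 and 24 months

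*Combined protocol and SAP*

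**What the plan says.** Section 8.4 collects "Hemoglobin, creatinine, liver function test (AST, ALT, Bilirubin) at baseline, day 7, day 14 and during long term follow up visits". Section 18.5 lists the same tests for the 6, 12 and 24 month visits: "Laboratory Tests: ALT, AST, Total Bilirubin, Creatinine, and Hemoglobin". The secondary objective in section 18.2 is to "Evaluate cardiac, hepatic and renal outcomes, quality of life, and long-term neurocognitive impairment of COVID-19 patients", so creatinine and the liver tests serve a named objective. Hemoglobin is measured but not named there.

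Section 18.8.3 describes the model: "Analyses will focus on longitudinal trajectories of change for outcomes specified in objectives 1-3". It continues: "Generalized linear multilevel models will evaluate change as a function of time, treatment, and the interaction of treatment and time after controlling for stratification variables". The variables are then named, so that adjustment is made "after controlling for stratification variables (i.e. site and baseline severity as measured by the MSOFA" cut at 4. The abbreviation i.e. makes this a closed list, and section 18.8.1 repeats it for the primary long-term outcome. Section 18.8.2 says that estimation centres on the treatment-by-time interaction. It gives d = 0.2, n = 180 after attrition, a posterior threshold of 0.80 and power of 92%, all for pulmonary function.

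Section 13.2 has a general rule. A baseline variable that differs between arms (posterior probability above 95%) and correlates with outcome triggers two analyses, one with it and one without.

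**The concern.** A plan to model change in creatinine or a liver enzyme should say what happens to the value measured before treatment. Section 18.8.3 does not. Read literally, the only pre-treatment information in the model is site and a dichotomised severity score.

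That score is a weak stand-in. Under the MSOFA table in section 5.1.2, an SpO2/FiO2 of 150 or less scores 4 on its own, and so does creatinine above 5.0 mg/dL. A severely hypoxemic patient with normal kidneys can therefore share a stratum with a maintenance-dialysis patient, whom exclusion 7 leaves eligible. Liver is scored only by visible jaundice. AST, ALT and hemoglobin do not appear.

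Two things are at stake. One is precision for the difference in level between arms. The other is that a chance difference in prior renal or hepatic function passes into the estimated treatment difference. The long-term group is about 200 of 650 randomized patients who agreed to return, some of them re-consented later (section 18.9), so the balance created by randomization is less secure there.

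**Working it through.** **Inputs.** From section 18.8.2: d = 0.2; 180 patients, taken as 90 per arm under 1:1 allocation; posterior threshold 0.80, treated as one-sided 0.20 under neutral weak priors (z = 0.842); within-patient correlation 0.3 at six months, halved for each further six months. Between months 6, 12 and 24 this gives 0.30, 0.15 and 0.075. Assumed: the baseline-to-visit correlation rho, which the documents do not give. Read rho as the correlation left after site and MSOFA stratum. Also assumed: d = 0.2 applies to the laboratory outcomes, since the plan states it only for pulmonary function.

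**The plan's own figure.** Power = Phi(delta/SE − 0.842), with SE from a generalized least-squares slope on the three visits. At 90 per arm, 92% needs a slope difference of 0.151 SD per six months, so SE = 0.151/(0.842 + 1.405) = 0.0672. The phrase about d = 0.2 developing linearly does not fix the slope:
- 0.2 reached at month 24 from randomization (0.05 per six months): 46%
- 0.2 per year (0.10): 74%
- 0.2 per six months (0.20): 98%

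The 92% is not reproduced at n = 180, but it is not shown wrong either. It serves below only as a starting value.

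**Level at one visit.** Power = Phi(0.2/sqrt((1 − rho²) × 2/90) − 0.842).
- rho = 0: Phi(1.342 − 0.842) = 69.1%
- rho = 0.3: Phi(1.406 − 0.842) = 71.4%
- rho = 0.5: Phi(1.549 − 0.842) = 76.0%

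**Level averaged over three visits.** The unadjusted variance of the mean is (3 + 2 × sum of pairwise correlations)/9. Adjustment subtracts the square of the mean baseline correlation.

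| Visit correlations | Baseline correlation | Variance | Power |
|---|---|---|---|
| 0.30/0.15/0.075 | unadjusted | 0.450 | 87.7% |
| 0.30/0.15/0.075 | plan's decay: 0.3, 0.15, 0.0375 (mean 0.1625) | 0.424 | 88.9% |
| 0.5 flat | unadjusted | 0.667 | 78.9% |
| 0.5 flat | 0.3 | 0.577 | 82.3% |
| 0.5 flat | 0.5 | 0.417 | 89.2% |
| 0.7 flat | unadjusted | 0.800 | 74.5% |
| 0.7 flat | 0.3 | 0.710 | 77.4% |
| 0.7 flat | 0.5 | 0.550 | 83.3% |

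The gains run from about 1 to about 10 points.

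**Treatment-by-time interaction.** A slope is a contrast whose weights sum to zero, so a term that is constant within a patient cancels. A baseline main effect leaves 92.0% at 92.0% in every scenario tried. Adding baseline-by-time gives 92.0% to 93.8%, or from an 80% start 80.0% to 82.7%. The upper ends occur when the baseline correlation decays over the visits.

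Baseline as a time-0 response behaves differently if one straight line runs from randomization. With separate baseline means per arm, power goes from 46.1% to 55.7% (0.2 at month 24) or from 74.1% to 87.0% (0.2 per year). That gain rests on linear divergence starting at a value taken in acute illness.

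**Imbalance.** The SE of a baseline difference is sqrt(2/90) = 0.149 SD. If section 13.2's 95% is read as one-directional with a flat prior, a difference below 1.645 × 0.149 = 0.245 SD triggers nothing. Unadjusted, it moves the level difference by up to 0.3 × 0.245 = 0.07 SD at rho = 0.3, or 0.5 × 0.245 = 0.12 SD at rho = 0.5, against a target of 0.2.

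**The case against.** The strongest reply is that the plan targets the interaction, and there a baseline covariate gains almost nothing. This stands. A stable imbalance in creatinine also shifts the level and not the slope, and the multilevel structure already absorbs stable differences between patients.

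A reader might infer that the plan discards the baseline values. The text does not establish that. It speaks of trajectories of change and does not list time points for each outcome. The months in section 18.8.2 belong to a pulmonary sample-size assumption. Baseline as the time-0 response is not excluded. The defect is silence.

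A reader might also pair the plan's visit correlations with a flat baseline correlation of 0.5 and report a rise from 88% to 98%. That combination is not coherent: an acute-illness value would predict month 24 (0.5) better than month 6 predicts month 12 (0.30). Extending the plan's own decay to baseline gives 87.7% to 88.9%.

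Section 13.2 does offer some protection, but it is conditional on the data and does not say which of its two analyses governs. Nor does the point extend to section 5.2, which lists "Creatinine, bilirubin, AST and ALT, hemoglobin" as safety measures and specifies no model to adjust.

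**Conclusion.** The point holds as a request to prespecify. Section 18.8.3 names site and MSOFA stratum, gives no role to the baseline laboratory values already collected, and section 13.2 would add them only after an imbalance is seen.

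For the treatment difference in level, adjustment is worth about 1 to 10 points of power under the assumptions shown, plus protection against chance imbalance among returners. As a covariate it is worth 0 to about 3 points for the interaction. These ranges depend on a baseline correlation that the documents do not supply. Values drawn during acute illness may correlate weakly with those at 6 to 24 months, which would put the gain at the low end, so no single power figure should be claimed.

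The matter is minor. It concerns secondary outcomes of an optional follow-up. The main trial's primary and secondary outcomes are untouched, and so is the long-term pulmonary outcome, for which no pre-treatment spirometry is listed.

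**What to change.** Add a sentence to section 18.8.3. For each long-term laboratory outcome with the same pre-treatment measurement, the patient's baseline value enters beside site and MSOFA stratum in one of two ways:
- as a covariate with a baseline-by-time term, on the log scale for creatinine, AST, ALT and bilirubin; or
- as the time-0 response, with the arms constrained equal at baseline.

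Name one and not both, since together they use the same value twice. If the time-0 route is chosen, state the assumed shape of the time course from randomization.

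The cost is that sentence; no visit or test is added. There is a small downside: because maintenance-dialysis patients are eligible, a single linear term in log creatinine may fit poorly, so the covariate's form needs some care (for example, a dialysis indicator).

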18.9 Informed Consent

[figure not shown]
Patients enrolled in the vadadustat study after February 5, 2021 have had the option to participate in the extended follow-up. Only patients who provided consent for extended follow-up will be included in this study.

Patients who were enrolled to the vadadustat study prior to February 5, 2021 will be reconsented in order to participate. For these patients, an IRB approved letter was sent out to inform them of an opportunity to participate in the long-term follow-up. One week later, a study coordinator contacted these patients and provided additional information. For those patients that agreed to be part of the study, an electronic consent via RedCap was sent to the patient's email. Patients have the opportunity to review the informed consent form, provide personal information and sign.

19. Publication Plan

No publication or disclosure of study results will be permitted, except under the terms and conditions of a separate, written agreement between The University of Texas Health Science Center at Houston (the Sponsor) and the investigator and/or the investigator's institution. The Sponsor will have the opportunity to review and approve all proposed abstracts, manuscripts, or presentations regarding this study prior to submission for publication/presentation. Akebia will have the opportunity to review all proposed abstracts, manuscripts, or presentations regarding this study prior to submission for publication. Any information identified by the Sponsor and Akebia as confidential will be deleted prior to submission.

For all publications relating to the study, the institution will comply with recognized ethical standards concerning publications and authorship, including: Section II - "Ethical Considerations in the Conduct and Reporting of Research" of the Uniform Requirements for Manuscripts Submitted to Biomedical Journals, http://www.icmje.org/index.html#authorship, established by the International Committee of Medical Journal Editors.

References

Appelhoff, R. J., Tian, Y. M., Raval, R. R., Turley, H., Harris, A. L., Pugh, C. W., Ratcliffe, P. J., and Gleadle, J. M. (2004). Differential function of the prolyl hydroxylases PHD1, PHD2, and PHD3 in the regulation of hypoxia-inducible factor. J Biol Chem 279, 38458-38465.

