18.6.2 Transthoracic Echocardiography (TTE)

This test is the primary noninvasive imaging modality for quantitative and qualitative evaluation of cardiac anatomy and function using an ultrasound. This test will be performed by physicians, fellowship-trained in ultrasonography.

The study currently evaluates pulmonary function and cardiac function as part of the long term follow up protocol. There is currently no lung imagining as part of the follow up process. Previous literature has shown ultrasound is as accurate as computed tomography for interstitial lung disease, without the cost or ionizing radiation. We are adding lung ultrasound as a seamless addition to the echo portion of the long term follow up study. We anticipate this exam will add approximately five minutes to the ultrasound portion of the protocol. There are no known harms associated with lung ultrasound.

C60 probe using abdominal preset. Axial images obtained via cranial caudal sweep of the right and left hemi-thorax in the mid-clavicular, mid-axillary, and peri-scapular. De-identified video clips of each location will be saved. We will make notation of any unusual signature with particular attention to previously described findings in COVID lung disease including B lines and sub-pleural consolidations.

Data Collection Sheet:

	R Midclav	L Midclav	R Midax	L Midax	R Periscap	L Periscap
3+ B lines						
Confluent B						
Lines						
Sub-pleural						
Conolidation						
Pleural						
Effusion						

Check mark indicates present of the finding

Other findings:

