18.8 Statistics

18.8.1 Specific Statistical Hypothesis of Primary Outcome

The primary outcome analysis will model pulmonary capacity as a function of time, treatment and the interaction of time and treatment after controlling for stratification variables (i.e. site and MSOFA < 4 or \ge 4).

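### The long-term model has no enrolment-era term, although late re-consent and the one-month visit window may leave early patients without a month-6 value and so bias the common time trend

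*Combined protocol and SAP*

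**What the plan says.** Section 18.5 ties consent for extended follow-up to one version of the consent form: "Informed consent for the extended follow-up shall be referenced to the IRB approved ICF of vadadustat study starting February 5, 2021". For anyone enrolled before that date, Section 18.9 says "Patients who were enrolled to the vadadustat study prior to February 5, 2021 will be reconsented in order to participate". The route was a letter ("an IRB approved letter was sent out to inform them of an opportunity to participate in the long-term follow-up"), contact by a coordinator one week later, and an electronic consent. No calendar date is given for the letter or the re-consents.

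Assessments are at three visits: "The following will be collected on the 6th, 12th and 24th month follow-up" (18.5). Section 18.6 allows one month after each due date and adds: "If a patient cannot be scheduled within one month of their follow up date, this will be deemed a loss to follow up". It does not say whether the visit or the patient is then lost.

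The primary long-term objective in 18.2 is "Evaluation of pulmonary capacity as a function of treatment, time and the interaction of treatment and time". Section 18.8.1 models pulmonary capacity as a "function of time, treatment and the interaction of time and treatment after controlling for stratification variables", these being site and MSOFA below 4 versus 4 or more. Section 18.8.3 repeats the same adjustment. Section 18 contains no term for enrolment date and no rule for visits already past when a patient re-consents.

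**The concern.** Patients who joined under the new form could attend all three visits. An earlier patient whose month-6 window had closed before re-consent could attend only the later ones. If that happened to an appreciable number, the month-6 mean comes from a different mix of patients than the month-12 and month-24 means. Any difference in lung function between eras, whether from case mix, care or survival, would then look like change over time.

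Time is itself part of the primary long-term objective, and Section 18.1 sets out to characterise long-term sequelae. A distorted common trend therefore affects a declared target even if the treatment comparison is untouched.

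The missing-data approach in Section 13.2 is described as robust to ignorable missingness. Here the gap at month 6 is driven by enrolment date. If lung function also varies with enrolment date, the gap is ignorable only once that date is in the model.

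**Working it through.** **1. Who can lack month 6.** The window closes 6 + 1 = 7 months after randomisation.

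| Re-consent date (assumed) | Month 6 closed for patients randomised before about |
|---|---|
| 5 February 2021 | 5 July 2020 |
| 1 month later | early August 2020 |
| 3 months later | early October 2020 |
| 6 months later | early January 2021 |

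Month 12 is lost as well if re-consent comes more than 12 + 1 = 13 months after randomisation. Without the actual dates, the early patients lacking month 6 range from none to most.

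**2. Inputs from the plan.** n = 180, from N = 200 less 10% attrition (18.8.2). Allocation 1:1 (Section 4). Visits at 6, 12 and 24 months. Correlation 0.3 at a six-month lag, halving for each further six months: 0.30 (6-12), 0.15 (12-24), 0.075 (6-24). The posterior threshold of 0.80 for the interaction is about one-sided 20% under flat priors.

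The plan gives no figure for era bias. Its nearest figure, 92% power, could not be reproduced: with these correlations, power runs from 46% to 98.4% according to how d = 0.2 is scaled over time, and 18.8.2 does not fix that scale. This is a separate reporting gap, and nothing below uses the 92%.

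**3. Assumptions, not in the documents.** Early share p = 20-50%. Fraction m = 50-100% of early patients without month 6, equal in both arms. Eras differ by δ = 0.2-0.4 SD at every visit. No true change over time.

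**4. Shift in the mix.** The early share is p at months 12 and 24, but p(1 − m)/(1 − pm) at month 6. For p = 0.5 and m = 1 it is 0 at month 6 against 0.5 later, so at δ = 0.2 the raw mean moves by 0.5 × 0.2 = 0.10 SD. For p = 0.2 and m = 0.5 it is 0.1/0.9 = 0.111 against 0.2, so the raw mean moves by 0.089 × 0.2 = 0.018 SD.

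**5. What the model reports.** The expected generalised least squares estimate is (Σ w X′V⁻¹X)⁻¹ Σ w X′V⁻¹μ. The sum runs over arm and three groups: early complete, early without month 6, and late complete. Within-patient correlation recovers part of the raw shift. Bias in the common slope over months 6-24, in SD:

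| p | m | δ = 0.2 | δ = 0.4 | SE |
|---|---|---|---|---|
| 20% | 50% | 0.010 | 0.021 | 0.103 |
| 20% | 100% | 0.022 | 0.045 | 0.105 |
| 50% | 50% | 0.018 | 0.036 | 0.107 |
| 50% | 100% | 0.044 | 0.089 | 0.115 |

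With an era term the bias is 0.000 in every row. The SE rises by about 2% at most (0.1147 to 0.1172 in the last row).

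**6. Treatment-by-time interaction.**
- *Era shifts the level only.* Both arms carry the same slope bias, so the difference between arms is 0.000 and the false-finding rate stays at 20%.
- *The treatment effect differs by era by 0.2-0.4 SD.* The interaction bias equals the slope bias for a shift of that size, 0.010-0.089 SD, with SE 0.206-0.229. The false-finding rate is 1 − Φ(0.842 − bias/SE). At the low end, 0.0104/0.2058 = 0.05, which gives 21%. At the high end, 0.0888/0.2294 = 0.387, and 1 − Φ(0.455) gives 32%.
- *Which term helps.* An era main effect leaves this interaction bias unchanged. Adding era-by-treatment brings it to 0.000.

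**The case against.** The strongest reply is that nobody can tell from the documents that anything is lost. If first randomisation was not much before July 2020 and re-consent was prompt, hardly any early patient misses month 6. If a missed window loses the patient and not just the visit, that patient does not contribute at months 12 or 24 either, and the mix does not shift. Months 12 and 24 in any case contain only those early patients who re-consented. All of this stands. A reader might infer that month 6 under-represents the early cohort by design, but the documents support only that it may.

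Second, 18.8.2 says estimation focuses on the interaction, and randomisation protects it from an era difference in level. That stands too. A reader might infer that the treatment comparison is compromised. This would need a treatment effect that differs by era, for which the documents offer no evidence, or re-consent that differs by arm. It would also be wrong to judge the slope bias against d = 0.2 or the 0.80 threshold, because the plan sets both for the interaction. The 20% baseline is itself a flat-prior approximation, while 18.8.3 specifies neutral, weakly informative priors.

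Third, Section 13.2 promises joint modelling, missing-data sensitivity analyses and pattern-mixture methods, and site adjustment may absorb part of an era difference because the first 30 patients came from two sites (8.1). This helps only in part. Section 13.2 does not name enrolment date, 18.8 does not repeat the provisions, and site is an imperfect stand-in for era.

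Finally, a reader might extend the point to lung ultrasound, since 18.6.2 says "We are adding lung ultrasound as a seamless addition to the echo portion of the long term follow up study". No introduction date is given and ultrasound is not the primary measure, so no restriction on its reporting follows.

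**Conclusion.** The concern holds in a limited form. The plan's rules make enrolment date a potential cause of missing month-6 values, and the model omits it. If lung function differs by era, the common time trend is biased, by about 0.01-0.09 SD over months 6-24 under the assumed shares and era differences. If no early patient's window had closed, or the eras do not differ, the bias is zero.

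The interaction is unbiased under a level shift. It moves by 0.01-0.09 SD, with a false-finding rate of about 21-32% instead of 20%, only if the treatment effect differs by era by 0.2-0.4 SD; differential re-consent by arm is a further route that is not quantified here. This does not show that the long-term treatment comparison is invalid. It is a gap worth closing because time is in the stated objective and the remedy is cheap.

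**What to change.** - In 18.8.1 and 18.8.3, add enrolment era as a fixed covariate: before versus from 5 February 2021, or calendar month of randomisation.
- Add two sensitivity analyses: one with an era-by-treatment term, and one limited to patients for whom all three visits were still possible when they consented.
- In 18.6, state that a visit whose window closed before re-consent is missing for that visit only.
- Report the numbers contributing at each visit by era and arm, so that the extent of the problem can be seen.

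The cost is SAP and protocol wording, one extra coefficient (two in the sensitivity model) and a negligible loss of precision. No new data are needed, since randomisation and consent dates should already be on file.
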